9.3 Clinical Laboratory Evaluations

Laboratory data will be presented using units as reported by the clinical laboratory.

The laboratory categories and parameters as defined in the protocol will include the tests listed in **Table 9-1 List of Laboratory Tests**.

The following listings will be presented:

- All laboratory values by category
- Out-of-range laboratory values
- Clinically significant laboratory values

For protocol-specified laboratory parameters, summary tables on observed and change from baseline values will be presented by treatment and visit for each category. Summary statistics will be presented for each laboratory test.

Table 9-1 List of Laboratory Tests

Laboratory Test Panel	Description
General biochemistry:	Alanine aminotransferase, aspartate aminotransferase, albumin, alkaline phosphatase, bilirubin total, chloride, creatinine (including eGFR using the MDRD equation), glucose, potassium, sodium, BUN, magnesium, calcium
Endocrinology	FSH
Hematology:	White cell count with differential (absolute values of neutrophil, lymphocyte, monocyte, eosinophil, and basophil), red cell count, hemoglobin, hematocrit, mean corpuscular volume, and platelet count
Coagulation tests:	Activated partial thromboplastin time, prothrombin time, INR
Serology:	HIV Ag/Ab Combo, Hepatitis B surface antigen and Hepatitis C virus,
Urinalysis:	Color, clarity, specific gravity, pH, leukocyte, protein, glucose, ketones, bilirubin, blood, nitrite, urobilinogen. Microscopic examination will only be performed if the dipstick test is outside of the reference range for leukocyte, blood, nitrite or protein

Abbreviations: BUN = blood urea nitrogen; eGFR = estimated glomerular filtration rate; FSH = follicle stimulating hormone; INR = international normalization ratio; MDRD = Modification of Diet in Renal Disease

9.4 Vital Signs

Vital signs will include systolic and diastolic blood pressures, pulse rate, and body temperature.

The following listings will be presented:

- All vital signs
- Clinically significant vital signs

Summary tables on observed and change from baseline values will be presented by treatment, visit, and/or timepoint.

9.5 12-lead Safety Electrocardiogram

Resting 12-lead safety Electrocardiogram results: Standard safety 12-lead ECGs will be performed as described in the CSP.

The 12-lead safety ECG results will be listed for each subject. All 12-lead safety ECGs will be evaluated for HR, and for PR, time elapsed between two successive R-waves of the QRS signal on the ECG (RR), QRS, QT, and QTcF intervals, and an investigator will judge the overall interpretation as normal or abnormal. If abnormal, it will be decided whether the abnormality is clinically significant or not clinically significant, and the reason for the abnormality will be recorded. The date/time, physician interpretation (normal, abnormal clinically significant, abnormal not clinically significant), and all evaluated parameters and intervals will be recorded in the electronic CRF (eCRF), and the paper printouts will be stored at the site. An investigator (or designee) will evaluate the printout of the 12-lead ECG in real time, and with particular attention to the effects of clinical importance on the PR, QRS, and QTcF intervals. Timepoints for 12-lead safety ECG measurements are specified in the CSP. The results per time point and for extra unscheduled ECGs requested by PI (Normal/Abnormal and CS or NCS, if CS it will be specified) from the 12-lead safety ECG will be listed for each subject.

The following listings will be presented:

- All ECGs
- Clinically significant ECGs

Summary tables on observed and change from baseline values will be presented by treatment, visit, and/or timepoint.

9.6 Telemetry Results

Telemetry results will be reviewed by the investigator, listed by date and time, described and reported, if considered clinically significant.

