The multiple ascending dose (MAD) study of AZD4041 (Protocol D7460C00002) has recently completed in Canada and interim data [blinded to treatment assignment] are available pending database lock. Three dose levels of AZD4041 were explored (CC ) in healthy volunteers, who received repeat once-daily doses for 14 days (N=12 subjects per cohort with N=9 receiving AZD4041 and N=3 receiving placebo). Cardiac monitoring included extended periods of ECG telemetry and Holter ECG recording. Dose escalation proceeded uneventfully across the cohorts. Exposures for AZD4041 (Cmax and AUC) increased in an approximate dose proportionate manner from CCI and remained within the range predicted. Maximum exposures (Tmax) were observed between 0.5 to 3.0 hours postdose. The effective half-life for AZD4041 ranged from 18.6 to 21.3 hours, comparable to that observed in the SAD study. Accumulation ratios over the dosing period ranged from 1.27 to 1.59 for  $C_{max}$ and from 1.66 to 1.81 for AUC. Steady state exposures (Ctrough) were achieved at Day 6 for the dose and Day 8 for the CCI dose levels. With respect to the pre-defined limits of human exposure and exposure predictions for potential doses higher than CCL, further dose escalation was not undertaken. No medically important tolerability or safety issues were raised by the dose escalation committee with respect to any of the safety endpoints (including vital signs, 12-lead ECGs, safety blood tests and urinalysis) during the course of the study. There were no observed SAEs or dose-limiting toxicities. Adverse events were mild in nature and were mostly resolved by checkout. The most common TEAEs, reported in two or more subjects, were NSVT (observed for two subjects in Cohort 1 [CCI placebo] and one subject in Cohort 3 [CC] placebo]), post lumbar puncture syndrome, medical device site reaction, headache, and nausea. The NSVT events were detected on Holter ECG monitoring; they were non-sustained and resolved spontaneously. One of the subjects with NSVT in Cohort 1 reported palpitations on Day 2 and was withdrawn by the Investigator before dosing on (Day 3) for safety reasons due to these adverse events. In Cohort 3 CCI placebo), one episode of NSVT was observed on Day 2, ~7.5 hours after dosing. The event was asymptomatic and resolved without intervention or recurrence. No clinically significant changes or trends for changes were observed for laboratory safety assessments, vital sign parameters, or ECG intervals in the MAD study. Overall, AZD4041 was considered to have a good safety and tolerability profile when

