# 6.1.6.2. Electronic Capture of 12-lead Continuous Digital Electrocardiogram

The AZ ECG Center will perform the dECG analysis, using the EClysis© system, version 4.0, or higher. Lead V2 will be used as the primary analysis lead, with lead V5 as the primary backup lead and lead II as the secondary back-up lead, for all time points when lead V2 is found to be unsuitable for analysis.

At clinical study protocol-indicated time points in Table 6-6, 12-lead continuous dECG files will be recorded using the 12-lead Mortara Holter equipment (H12+) according to AZ ECG Center's standard procedures for settings/configuration, recording and transfer of dECGs. The 12-lead Holter memory cards will be sent to the AZ ECG Center with an agreed courier.

It is to be noted that the 12-lead Holter recordings will serve multiple purposes. It will be the source for 12-lead dECG extractions. In addition to providing 12-lead dECG extractions, the recordings will be used for prolonged arrhythmia monitoring as part of the safety data collection (these data will be analyzed at a later stage and will not be available for the bedside safety monitoring at site). The first ECG recording with Holter device starts on Day -1 (approximately 24 hours before dosing) and continues to 72 hours postdose (Day 4). On Day 8, recording will start at least 1 hour before dosing and continue to 24 hours postdose. On Day 15, recording will start at least 1 hour before dosing and continue to 72 hours postdose (Day 18). Specific extraction times for dECG are presented in Table 6-6.

The same recording device will be used for each subject at all time points, when possible. Date and time settings must be checked on the Mortara Holter equipment, at the start of each study

day and aligned with an official timekeeper. The metadata of each file will be checked by the responsible personnel at the study site to ensure that the cards sent to the AZ central dECG files repository have correct metadata.

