Skin preparation must be thorough and electrode positions must be according to standard 12-lead ECG placement. Permanent electrodes will be applied at least 30 minutes before first study recording and left in place for the duration of each relevant study day. Electrode positions for dECG take precedence over those for telemetry. Subjects will rest in a supine position for at least 5 to 10 minutes before the start of each recording. A shorter resting period (at least 5 minutes) may be done in certain cases, depending on competing procedures in the study.

The subject should be in the same supine body position (maximum 30 degrees flexion of the hip and feet not in contact with the footboard) at each recording time point during the study.

From the continuous dECG files received at the AZ ECG Centre, the EClysis© system will extract continuous files of at least 5 minutes length at clinical study protocol-indicated time points in Table 6-6. The extraction window can be adjusted by the responsible ECG Scientific Advisor during the Metadata approval procedure, based on the 'Clinical Logs' received from the site. As standard, from each dECG extracted window, 10-second ECGs will then be extracted by the EClysis© system twice per minute and automatically analyzed by the software. The ECG Scientific Advisor will perform all necessary manual corrections of the ECG annotations provided automatically by EClysis©. All dECGs from 1 subject will be analyzed by a single reader in a blinded manner.

The AZ ECG Centre Cardiologist will finally review all data and perform all necessary adjustments before locking the data into a read-only state. From the locked data, the numerical values for the ECG intervals and amplitudes will then be made accessible on a secure file share of the AZ dECG central repository to accredited Data Management specialists for conversion into SAS® files.

The following dECG variables will be reported by the AZ ECG Centre: RR, PR, QRS, and QT intervals from the lead, defined as the primary analysis lead, as well as potential T-wave morphology changes.

Derived parameters (QTcF, HR, and others, as applicable) are calculated by the study statistician or delegate.

Study		ECG	Time: Start of the Extraction Window,	D	Time: Stop of the Extraction Window,	dECG	
Day	Number	Number	Hour:Min a,b	Dose	Hour:Min	Continuous c, d, e	Other f
1	2		-02:00		-01:30		Apply electrodes

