An AE of special interest (AESI: serious or non-serious) is one of scientific and medical concern specific to the Sponsor's drug product, for which ongoing monitoring and rapid communication by the Investigator to the Sponsor may be appropriate. An AESI is a noteworthy event for the particular product or class of products that a Sponsor may want to monitor carefully. It could be serious or non-serious (eg, hair loss, loss of taste, impotence), and could include events that might be potential precursors or prodromes for more serious medical conditions in susceptible individuals. Such events may require further investigation in order to characterize and understand it. Depending on the nature of the event, rapid communication by the Sponsor to other parties (eg, regulatory authorities) might also be warranted.

The following AESI(s) has been specified for the study intervention(s) in this protocol:

• Cardiac arrhythmia (including NSVT)

Non-serious AESIs are to be recorded in electronic data capture (EDC) within 72 hours, and serious AESIs are to be reported to the sponsor within 24 hours.

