2 STUDY OBJECTIVES

The objectives of the study and corresponding study endpoints are detailed in [Table 2-1](#).

Table 2-1 Objectives and Related Endpoints

Objective	Endpoint
Primary	
To assess the effect on respiratory drive of morphine administered after multiple doses of AZD4041 compared to morphine administered alone in healthy recreational opioid users	
 • EtCO₂ (mmHg): Incidence of increased EtCO₂ of at least 10 mmHg compared to baseline or >50 mmHg (sustained for at least 30 seconds) • SpO₂ (%): Incidence of reduction in SpO₂ to <92% (sustained for at least 30 seconds)
Secondary	
 • SpO₂ (%) ▪ Mean time to reduction in SpO₂ to <92% (sustained for at least 30 seconds) ▪ Mean duration of reduction in SpO₂ to <92% (sustained for at least 30 seconds) ▪ Maximum postdose reduction of SpO₂ adjusted for baseline ▪ Mean postdose SpO₂ • EtCO₂ (mmHg) ▪ Mean time to each increased EtCO₂ episode of at least 10 mmHg compared to baseline or >50 mmHg (sustained for at least 30 seconds) ▪ Mean duration of each increased EtCO₂ episode of at least 10 mmHg compared to baseline or >50 mmHg (sustained for at least 30 seconds) ▪ Maximum postdose increase in EtCO₂ adjusted for baseline ▪ Mean postdose EtCO₂

	
 • Respiratory rate (breaths/min) ▪ Incidence of reduced respiratory rate to <6 breaths/min (sustained for at least 30 seconds) ▪ Mean time to each reduced respiratory rate episode of <6 breaths/min (sustained for at least 30 seconds) ▪ Mean duration of each reduced respiratory rate episode of <6 breaths/min (sustained for at least 30 seconds) ▪ Maximum postdose decrease in respiratory rate adjusted for baseline ▪ Mean postdose respiratory rate • Incidence, frequency, severity, and relationship of AEs • Vital signs (blood pressure, heart rate, and oral temperature) • ECGs (12-lead safety ECGs, 12-lead digital ECGs, and ECG telemetry) • Clinical laboratory test results (clinical chemistry, hematology, coagulation, urinalysis) • Neurological examination findings • Columbia Suicide Severity Rating Scale (C-SSRS) findings • Physical examination findings • Type of medical intervention used, summarized for each event of significantly increased EtCO₂, reduced SpO₂, or reduced respiratory rate

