5 DATA HANDLING AND PRESENTATION

5.1 Safety Analysis Presentation

Adverse events and medical history will be classified using the Medical Dictionary for Regulatory Activities (MedDRA) terminology as defined in the study Data Management Plan (DMP).

Prior and concomitant medications will be coded with the World Health Organization Drug Dictionary (WHODrug) as defined in the study DMP.

In general, all safety summary tables will be presented for the safety population. Summaries for AEs will be presented by treatment and treatment sequence. Summaries for other safety endpoints will be presented by treatment if the endpoints are measured at the end of each period or by treatment sequence if the endpoints are not measured at the end of each period (End of Study only).

In general, the data listings will include all subjects in the safety population up to the point of study completion or discontinuation; exceptions will be listings pertaining to a subset of subjects only (eg, subjects with protocol deviations) or a subset of records/events (eg, abnormal laboratory values). Limited data for those not included in the safety population, eg, who failed screening, may be presented, as appropriate.

Categorical variables will be summarized using sample size (N), number of available data (n), and the percentage of available data (%) for each class. Continuous variables will be summarized using descriptive statistics, including N, n, arithmetic mean (mean), standard deviation (SD), minimum (min), median, and maximum (max).

The following general considerations may be applied:

- Study Day will be derived from the reference date (eg, the day of the first dose of study drug) and date of event as:
Study Day = (date of event – reference date) +1, if event is on or after the reference date;
Study Day = date of event – reference date, if event is before the reference date.
- Duration will be calculated using the general formula: (end date - start date) +1.

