- 2) (predose): Morphine + AZD4041 (predose average Days 2-15) vs (predose): Morphine + Placebo (predose average Days 2-15)

9.2 12-lead digital ECG Statistical Methodology

From the dECG data, the following parameters will be derived:

- 1) QTcF will be calculated as QTcF = QT*RR^{-1/3}, where the QT interval is in milliseconds and the RR interval is in seconds.
- 2) Heart rate will be calculated, based on the RR interval as HR = 60/RR interval, where the RR interval is in seconds.
- 3) Calculation of derived parameters will be performed after smoothing of QT and RR data.

The dECG data will be smoothed on an individual basis before performing the derivations above and prior to calculation of any changes from baseline or descriptive statistics. For each subject it will be done as follows: the mean value of all the measurements will be taken provided that at least 4 measurements are present and the time between the first and last is greater than 2.75 minutes or else, the smoothed value at the corresponding target time point will be set to missing.

Digital ECG results will be listed by treatment (Morphine and AZD4041 vs Morphine and placebo) for each subject and time point and will include all individual and smoothed values of PR, RR, QRS, QT interval, and the derived values of QTcF and HR. All smoothed and derived

parameters will have changes from baseline derived and presented within subject and treatment group.

Descriptive statistics will be presented by treatment arm and time point for smoothed values and changes from baseline of smoothed values of PR, RR, QRS, QT; derived values and changes from baseline for QTcF and HR will also be included. The baseline for the dECG measurements will be the (smoothed) predose assessment on Day 1.

Outliers with respect to PR, QRS, HR, RR and QTcF will also be tabulated for the following categories, described below.

For QTcF these values will be reported per time point:

- Absolute value > 450 ms and ≤ 480 ms
- Absolute value > 480 ms and ≤ 500 ms
- Absolute value > 500 ms
- Increase from baseline > 30 ms and ≤ 60 ms
- Increase from baseline > 60 ms

The maximum postdose values for PR interval will be summarized by treatment according to the following categories:

- ≤ 220 ms
- > 220 and ≤ 240 ms (all instances flagged in the listing*)
- > 240 ms (all instances flagged in the listing **)

The maximum postdose values for QRS duration will be summarized by treatment according to the following categories:

- ≤ 115 ms

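### The SAP has no AESI table and no output for Holter arrhythmia data, and its telemetry rule is filtered and ambiguous, so the AZD4041-versus-placebo count for the only AESI may be incomplete

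*SAP*

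**What the plan says.** **Status of the event.** Protocol 7.1 names one AESI, "Cardiac arrhythmia (including NSVT"). SAP Table 2-1 lists telemetry within a secondary safety endpoint: "ECGs (12-lead safety ECGs, 12-lead digital ECGs, and ECG telemetry").

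**Holter.** Protocol 6.1.6.2 says the "recordings will be used for prolonged arrhythmia monitoring as part of the safety data collection". It adds that these data will be analysed later and will not be available for bedside monitoring. Recording runs from Day -1 to Day 4, from Day 8 for 24 hours after dosing, and from Day 15 to Day 18. The variables the ECG Centre is to report are "RR, PR, QRS, and QT intervals from the lead, defined as the primary analysis lead, as well as potential T-wave morphology changes". SAP 9.2 follows that list: "Outliers with respect to PR, QRS, HR, RR and QTcF will also be tabulated for the following categories". The SAP mentions Holter only in an Appendix A footnote about replacing the memory card.

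**Telemetry.** SAP 9.6 is a single sentence: "Telemetry results will be reviewed by the investigator, listed by date and time, described and reported, if considered clinically significant".

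**Adverse events.** SAP 5.1 states: "Summaries for AEs will be presented by treatment and treatment sequence". SAP 9.8 tabulates treatment-emergent events by system organ class, preferred term and treatment. Protocol 7.4 sends post-dose events to the adverse event page and mentions non-serious AESIs alongside them. No SAP section has an AESI table or listing.

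**The concern.** NSVT is the programme's open cardiac question. Protocol 1.3.2 reports it in both earlier human studies. In the single-dose study both episodes were asymptomatic and self-resolving. Of the multiple-dose study the protocol says: "The NSVT events were detected on Holter ECG monitoring; they were non-sustained and resolved spontaneously". The blinded multiple-dose count cannot separate drug from background.

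This trial has a concurrent placebo sequence and prolonged recording in both sequences, so it can show the two side by side. The plan provides for that only through the adverse event tables. Those tables hold what was recognised and entered as an event. Brief, silent runs found on a recording read later are the kind most likely to be left out, and the documents give no route by which they get in. At stake is whether the report can state how many subjects in each sequence had the arrhythmia the protocol singled out.

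**Working it through.** The plan gives no sample size, power or target rate for arrhythmia, so there is no planned figure to reproduce. The check traces the text and then sizes the gap.

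**1. Can the planned digital ECG output detect NSVT?** Mostly not. SAP 9.2 averages each extraction window into one smoothed interval value. In Protocol Table 6-6, the Day 15 to Day 18 extractions are one of 10 minutes and eleven of 5 minutes: 10 + 11 × 5 = 65 minutes. The recording runs from at least 1 hour before dosing to 72 hours after, at least 73 × 60 = 4,380 minutes. 65 / 4,380 = 1.5%. The rest of the recording has no planned output.

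**2. Does telemetry fill the gap?** Not by comparison between arms. SAP 9.5, on safety ECGs, plans a listing of all results, a listing of significant ones, and summary tables by treatment. SAP 9.6 plans no table. Its closing condition may govern the whole sentence or only the last verb. Protocol 6.1.7 asks that short, self-limiting, asymptomatic arrhythmias, ventricular tachycardia among them, be documented and evaluated. On the narrower reading SAP 9.6 would not carry all of these into the report.

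**3. Do the adverse event tables fill it?** Partly. Anything recorded as an event is shown by treatment and sequence. But Protocol 6.1.6.2 puts Holter arrhythmia data out of bedside reach, and Protocol 7.4 closes registration of new events 7 days after the last dose. No passage says whether, or how, a finding from a later Holter review becomes an event.

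**4. Earlier rates.**
- Single-dose study: 6 cohorts × 6 on AZD4041 = 36; 2/36 = 5.6%, matching the stated 5.6%.
- Multiple-dose study: 3 cohorts × 12 = 36; 3/36 = 8.3%. This pools blinded arms (27 AZD4041, 9 placebo). The AZD4041 rate could be anything from 0/27 = 0% to 3/27 = 11.1%.

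**5. Expected numbers here** (28 in Sequence 1, 16 in Sequence 2), taking 5.6% to 8.3% as an assumed range:
- Expected subjects among 28: 28 × 2/36 = 1.6; 28 × 3/36 = 2.3.
- Chance of at least one, 1 − (1 − p)^28: 80% to 91%.
- One missed subject lowers Sequence 1 incidence by 1/28 = 3.6 points, or 1/2.33 = 43% to 1/1.56 = 64% of the expected count.
- If both sequences capture the same fraction c of true cases, the displayed risk difference is c times the true one.

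**6. What a complete count could show.**
- Exact 95% upper limit for zero events, 1 − 0.025^(1/n): 12.3% for 0/28 and 20.6% for 0/16.
- 2/28 against 0/16: difference 7.1 points. Wilson limits are 2.0% to 22.6% and 0% to 19.4%. Newcombe lower limit: 7.1 − √(5.2² + 19.4²) = −12.9. Upper limit: 7.1 + (22.6 − 7.1) = +22.6.
- Fisher's exact test reaches p ≤ 0.05 only from 7/28 against 0/16 (p = 0.037). Power at 5.6% against 0% is 0.1%, and at 8.3% against 0% it is 0.7%.

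At least one event is likely, and a formal test would be uninformative. The value lies in a complete count with an interval.

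**The case against.** The strongest reply is that the comparison already exists. AESIs may be serious or non-serious, Protocol 7.1 sets no clinical-significance threshold for them and asks for entry within 72 hours, and event tables are split by treatment and sequence. The programme's history supports this. The single-dose 5.6% is itself a treatment-emergent event rate for asymptomatic episodes, and the Holter-detected events of the multiple-dose study were also reported as treatment-emergent. SAP 9.6 removes nothing from those tables, and SAP 9.8 says all available data will be listed unless otherwise specified, which favours the milder reading of the telemetry sentence.

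Much of this stands. A reader might infer that the AESI is never compared with placebo, or that the telemetry condition could erase the whole signal. The documents support neither, because recorded arrhythmias are displayed by arm. What the reply does not supply is a rule in these documents that repeats the earlier practice, or any count that can be checked against the recordings. A listing is not a comparison.

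Two further points stand. Exclusion criterion 18 removes subjects with couplets or any ventricular tachycardia on predose 24-hour telemetry, so Day -1 is selected towards few events and is a poor estimate of background; the concurrent placebo sequence matters more. And a reader might assume that a full central Holter read for arrhythmia is already planned. Protocol 6.1.6.2 specifies central reading for the digital ECG extractions and names no reader for arrhythmia.

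**Conclusion.** The point holds as a gap in completeness and traceability. Under the plan as written, the between-arm display of the only AESI depends on what the site records as an event, while a stated purpose of the Holter recordings has no output. The comparison exists but is not reliably complete.

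The size is small in absolute terms and large in relative terms: one or two subjects, when about two are expected. That rests on an assumed rate of 5.6% to 8.3%, the upper end of which is not an AZD4041 rate. How many events would be missed cannot be calculated from the documents; it could be none if the site records every finding as it did before. The trial cannot settle whether AZD4041 causes NSVT, since even a complete 2/28 against 0/16 leaves an interval of about −13 to +23 points. The case is for an unfiltered descriptive count, worth making before database lock and unblinding.

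**What to change.** 1. **SAP 9.6.** Reword so that all telemetry arrhythmia findings are listed and reported whatever the clinical-significance judgement, with those judged significant flagged.
2. **One table and one listing.** Show subjects with NSVT or another AESI arrhythmia by source (Holter, telemetry, adverse event), sequence and period: Day 1 morphine, Days 2-4, Days 7-9 and Days 15-18. Give exact or score 95% confidence intervals, for estimation only and without a test. Show Day -1 for reference, with a footnote that exclusion criterion 18 selects it towards few events.
3. **Holter review.** State who performs the arrhythmia review foreseen in Protocol 6.1.6.2, when, and how its findings reach the analysis data.

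No clinical rule or recording schedule changes. The cost is SAP wording, one table, one listing and some data handling. The review effort depends on what arrangement exists for reading full recordings, which the documents do not say. The downside is that benign background arrhythmias will appear in the report; the placebo column puts them in context.
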